6.3.2 Symptom clusters based on the modified RDQ e-diary

Exploratory factor analysis will be undertaken in an attempt to study the underlying concepts in the modified RDQ for the morning and evening registrations combined as well as for the morning registrations separately using the following variables for each symptom:

- Number of days with symptom (having symptom defined as symptom intensity greater than “Did not have”) during the last seven days prior to visit 2. If registrations for two or more days are missing during the seven day period for a patient, the number of days with symptom will be set to missing.
- Mean symptom intensity during last seven days prior to visit 2. If registrations for two or more days are missing during the seven day period for a patient, the mean symptom intensity will be set to missing.
- Number of morning registrations with symptom during the last seven mornings prior to visit 2. If two or more morning registrations are missing during the seven day period for a patient, the number of mornings with symptom will be set to missing.
- Mean symptom intensity during last seven morning registrations prior to visit 2. If two or more morning registrations are missing during the seven day period for a patient, the mean symptom intensity will be set to missing.

Principal components factor analyses with varimax and oblimin rotation will be used. All loadings for the retained factors will be presented.

The selection of symptom clusters and corresponding variables to be evaluated in the second part of the study will be based on the evaluation of the exploratory factor analysis together with the other results from the first part of the study.

There are some items in the modified RDQ that are expected to describe the same symptom. The item ‘Heartburn’ is included to serve as a comparison to ‘A burning feeling behind the breastbone’. In the second part of the study, ‘A burning feeling behind the breastbone’ will be the item of choice. Based on the results from the first part of the study, one of the items

‘Unpleasant movement of material upwards from the stomach’ and ‘Stomach contents (liquid or food) moving upwards to your throat or mouth’ will be used moving forward.

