6.3.5.2 Internal consistency

The consistency of questions within the modified RDQ symptom clusters and modified QOLRAD clusters will be evaluated using Cronbach's alpha coefficient (Cronbach 1951). Cronbach's alpha will be estimated as

$$\alpha_c = \frac{m}{m-1} \left(1 - \frac{\sum Var(x_i)}{Var(\sum x_i)} \right)$$

where m is the number of items in the cluster, $Var(x_i)$ is the estimated variance of the i^{th} item and the summation is over all items within a cluster. Ninety five% confidence intervals for Cronbach's alpha coefficients will be presented. A high alpha coefficient suggests that the items within a cluster measure the same construct. A minimum value of 0.70 has been recommended (Fayers et al 2007).

For the modified RDQ, Cronbach's alpha will be calculated for each multi-item symptom cluster derived through the factor analysis of 24 h period values (see section 6.3.2. Item scores will be defined as the mean or maximum intensity (see section 6.3.1 of the last 7 days prior to visit 2.

For the modified QOLRAD, Cronbach's alpha will be calculated for each multi-item cluster derived through the factor analysis described in section 6.3.3, using the item responses at visit 2.

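### Part 1 alpha and validity are specified on clusters from all modified RDQ items, with no repeat on the items that go forward to Part 2

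*Protocol*

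**What the plan says.** All references are to the protocol; the SAP was not available.

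- **Redundant items (6.3.2).** The section states: "There are some items in the modified RDQ that are expected to describe the same symptom". Two pairs follow. On the first: "The item ‘Heartburn’ is included to serve as a comparison to ‘A burning feeling behind the breastbone", and "In the second part of the study, ‘A burning feeling behind the breastbone’ will be the item of choice". On the second: "Based on the results from the first part of the study, one of the items" describing upward movement of material or stomach contents will be used from then on.
- **Factor analysis (6.3.2).** It is run "using the following variables for each symptom". No item is excluded. Clusters for Part 2 are selected from this analysis together with the other Part 1 results.
- **Internal consistency (6.3.5.2).** "Cronbach's alpha will be calculated for each multi-item symptom cluster derived through the factor analysis of 24 h period values", with a confidence interval. A recommended minimum of 0.70 is cited.
- **Construct validity (6.3.6.1 and 6.3.6.2).** Convergent, discriminant and known-groups analyses use the derived symptom clusters, with a reference to 6.3.2.
- **Test-retest in Part 2 (6.5.1).** The ICC is also estimated for the derived clusters of 6.3.2.
- **Scope of the SAP (6.1).** The SAP is announced for analyses involving post-randomisation data. The Part 1 analyses are set out in the protocol itself.

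**The concern.** Part 1 is meant to establish the validity and reliability of the modified RDQ e-diary (3.2.1), and the study is to decide which symptoms form a future primary endpoint (2.1). That evidence should describe the score that will be used. The protocol knows in advance that two items will drop out, yet it specifies no reliability or validity analysis after they do.

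Two things follow if the plan is carried out as written. A cluster holding both members of a pair will show a higher alpha than the same cluster with one member. A pair can also form a component of its own, so the cluster structure may partly reflect the wording overlap. In either case the reported Part 1 properties would belong to a score that the study does not take forward.

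**Working it through.** **1. Order of the steps.** Section 6.3.2 ties the item reduction to the second part of the study and bases the regurgitation choice on Part 1 results. The alpha and validity analyses in 6.3.5.2 and 6.3.6 are themselves Part 1 results. On the plain reading they come before the reduction, and no later section repeats them.

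**2. The protocol's own alpha figure.** Section 6.6 assumes alpha 0.7, 2 items and 450 patients, and states about ±0.06. The log-transform interval is 1 − (1 − α)·exp(±1.96·√(2k/((k − 1)(n − 2)))). With k = 2 and n = 450 the root is √(4/448) = 0.0945. The limits are 0.639 and 0.751, a half-width of 0.056. The stated figure reproduces and is not in question.

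**3. Alpha with and without duplicates.** The protocol gives no inter-item correlations, so these are assumptions: r between different symptoms, d within a pair, and each duplicate loading with its partner. Standardised alpha is m/(m − 1)·(1 − m/S), where S is the sum of the m × m correlation matrix.

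- Two kept items: S = 2 + 2r.
- Two kept and one duplicate: S = 3 + 2d + 4r.
- Two kept and both duplicates: S = 4 + 4d + 8r.
- m distinct items: S = m + m(m − 1)r.

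At r = 0.40 and d = 0.8:

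- Two kept: 2·(1 − 2/2.8) = 0.571.
- One duplicate: 1.5·(1 − 3/6.2) = 0.774.
- Both duplicates: (4/3)·(1 − 4/10.4) = 0.821.

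Results over a range of r, with d = 0.8:

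| r | 2 kept | 3 distinct | 2 kept + 1 duplicate | 4 distinct | 2 kept + both duplicates |
|---|---|---|---|---|---|
| 0.30 | 0.46 | 0.56 | 0.72 | 0.63 | 0.78 |
| 0.40 | 0.57 | 0.67 | 0.77 | 0.73 | 0.82 |
| 0.50 | 0.67 | 0.75 | 0.82 | 0.80 | 0.86 |

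At r = 0.40, varying d from 0.7 to 0.9 gives 0.75 to 0.80 with one duplicate and 0.80 to 0.84 with both.

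**4. Splitting the rise at r = 0.40, d = 0.8.**

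- One duplicate: the rise is 0.203, of which 0.095 is item count (0.571 to 0.667) and 0.108 is duplication (0.667 to 0.774).
- Both duplicates: the rise is 0.249, of which 0.156 is item count (0.571 to 0.727) and 0.093 is duplication (0.727 to 0.821).

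The retained score loses the extra length as well as the duplication, so the whole gap separates the two scores.

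**5. A longer cluster.** Section 6.3.1 names a six-item heartburn and regurgitation set that contains both pairs; four items remain after reduction. For six items S = 6 + 4d + 26r. At r = 0.40 and d = 0.8 alpha is 1.2·(1 − 6/19.6) = 0.83, against 0.73 for the four.

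**6. A cluster made of one pair only.** Alpha is 2d/(1 + d): 0.82, 0.89 and 0.95 for d = 0.7, 0.8 and 0.9. After reduction one item is left and alpha is undefined.

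**7. Factor structure.** Assume one common correlation r across the 13 items, except d = 0.8 within the two pairs.

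| r | Leading eigenvalues, 13 items | Leading eigenvalues, 11 kept items |
|---|---|---|
| 0.20 | 3.62, 1.40, 1.18 | 3.00, 0.80 |
| 0.30 | 4.77, 1.20, 1.03 | 4.00, 0.70 |
| 0.40 | 5.93, 1.00, 0.87 | 5.00, 0.60 |

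The second and third components are raised by the pairs alone. Whether they would be retained depends on r and on the retention rule.

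**The case against.** **The clusters may already be the reduced ones.** The sentences dropping items stand in 6.3.2, and the later sections refer to 6.3.2 for the derived clusters. This reading is possible. It fits poorly with the reduction being tied to Part 2 and, for the regurgitation items, to Part 1 results. The two-item planning case in 6.6 does not settle it, since a duplicate pair is also a two-item cluster. What stands is that the text is not explicit, so the mismatch is something that may happen.

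**All items must enter the first factor analysis.** This stands in full. Heartburn is there as a comparator, and the regurgitation choice needs data on both items. A reader might infer that the full-item run is itself an error; the protocol's purpose does not support that.

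**0.70 is not a gate.** This also stands. A reader might infer from the table that a failing cluster would be passed. Section 6.3.5.2 cites 0.70 only as a recommended minimum, and 6.3.2 selects clusters on several Part 1 results together.

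**The illustration is favourable to the point.** In part. The correlations and the co-loading are assumed, and much of the rise is item count: at r = 0.40 four distinct items already exceed 0.70. The both-duplicates case also needs the burning-feeling and upward-movement items to be the only kept items of one cluster, whereas 4.2.1.1 places them in separate RDQ dimensions. The one-duplicate case is closer to those dimensions, which have two items each. In the six-against-four case at r = 0.40 the reduced score still reaches 0.73. No size can be given for the convergent or known-groups results.

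**Part 2 produces its own evidence.** Test-retest and responsiveness are assessed there, and details may sit in the SAP. That does not replace alpha or construct validity, which the protocol specifies only in Part 1.

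**Conclusion.** The point holds as a mismatch between the score validated in Part 1 and the score carried into Part 2. As written, alpha, convergent and known-groups results are computed on clusters from all items, and nothing repeats them on the items kept.

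The direction for alpha is clear where a duplicate shares a cluster with its partner; the size is conditional. Under between-symptom r = 0.40 and pair r = 0.8, the gap to the retained two-item score is 0.20 with one duplicate and 0.25 with both. For six items against four it is 0.11 (0.833 − 0.727). Each exceeds the ±0.06 precision planned in 6.6. Roughly half of the one-duplicate gap, and more than half of the two-duplicate gap, is item count.

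The documents do not show that the reported alpha will be inflated, only that the specified analysis leaves this open.

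**What to change.** 1. Keep the full-item factor analysis, and state that its purpose is to compare the paired items and choose the regurgitation item.
2. After that choice, refit the factor analysis without Heartburn and without the dropped regurgitation item.
3. Recompute alpha with its confidence interval, and the convergent and known-groups results, on the reduced clusters. Report these as the properties of the score, and compare alpha with the recommended 0.70 on that set.
4. State in 6.5.1 that the Part 2 test-retest uses the same reduced clusters.

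This needs no new data. The cost is one re-run of programs already planned and a reported alpha that may be lower.

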6.3.3 Factor analysis, modified QOLRAD

Exploratory factor analysis will be undertaken in an attempt to study the underlying concepts in the modified QOLRAD using the item responses at visit 1. Principal components factor analyses with varimax and oblimin rotation will be used. All loadings for the retained factors will be presented.

The factor structure of the modified QOLRAD will be compared to the original QOLRAD heartburn version. If a new factor structure for the modified QOLRAD is a better fit for the study population, this new factor structure will be used moving forward.

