4.2.5 The modified Quality of Life in Reflux And Dyspepsia (QOLRAD) questionnaire

The validity and reliability of the modified QOLRAD will be assessed in this study. In addition, specific impact dimensions (e.g. sleep and food/drink) will be used as reference when establishing the clinically meaningful change of the modified RDQ e-diary.

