4.2.5.1 Method of assessment

Patients will be asked to complete the modified QOLRAD (Appendix H) in an electronic format at visits 1, 2, 4 and 5 and in the case of early discontinuation.

The modified QOLRAD is a self-administered, disease-specific PRO instrument specifically developed to monitor changes in the impact of upper gastrointestinal symptoms on patients' daily lives (Wiklund et al 1998). The QOLRAD was developed in two versions, one for heartburn and one for dyspepsia. Based on a review of the literature, and a review of available and published Health Related Quality of Life questionnaires targeted towards patients with gastrointestinal symptoms a wide range of items was extracted. Data analysis of several

thousand patients with GERD and dyspepsia included in clinical trials completing the Psychological General Well-Being (PGWB) index yielded another set of valid items with confirmed ability to discriminate between items responsive to treatment-induced changes. Finally, a clinician evaluation of clinical relevance of the items selected according to the principles described previously was performed. After these procedures a draft questionnaire was developed. After focus group interviews of patients with a diagnosis of GERD or dyspepsia, performed in Canada and the US, items were added to the initial questionnaire (Wiklund et al 1998).

The QOLRAD consists of 25 items addressing concerns associated with gastrointestinal symptoms, combined into five dimensions:

- Emotional distress (items 12, 14, 15, 17, 19, 22)
- Sleep disturbance (items 8, 10, 11, 18, 21)
- Food/drink problems (items 3, 5, 9, 13, 16, 20)
- Physical/social functioning (items 2, 6, 23, 24, 25)
- Vitality (items 1, 4, 7)

Items are rated on a 7-graded Likert scale. Subscale scores are obtained by summing all item responses and dividing by the number of items (Wiklund et al 1998).

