6.3.5 Reliability

6.3.5.1 Test retest, modified QOLRAD

Test-retest reliability will be investigated for the modified QOLRAD using Intraclass Correlation Coefficients (ICC). The within-patient and between-patient mean square will be calculated by two-way analysis of variance (ANOVA) with the factors of patient and visit (1 and 2), using subjects in a stable condition between visit 1 and 2. A stable patients is defined as a patient who had “About the same”, “Almost the same, hardly worse at all” or “Almost the same, hardly better at all” on OTE at visit 2. The ICC will be calculated for the derived clusters of the modified QOLRAD obtained through the factor analysis described in section 6.3.3. A cluster score will be calculated as the mean value of the items in the cluster. Other ways of calculating cluster scores may be explored. The test-retest reliability intraclass correlation coefficient (R) will be estimated as:

$$\hat{R} = \frac{BMS - WMS}{BMS + (k_0 - 1)WMS}$$

where BMS and WMS are the mean square values between-patients and within-patients respectively, and k_0 denotes the number of replicates per patient (two in this case).

A 95% confidence interval for R will be estimated as

$$R \geq \frac{\frac{BMS}{WMS} - F_{N-1, K-N, \alpha/2}}{\frac{BMS}{WMS} + (2-1)F_{N-1, K-N, \alpha/2}}, \quad R \leq \frac{\frac{BMS}{WMS} - F_{N-1, K-N, 1-\alpha/2}}{\frac{BMS}{WMS} + (2-1)F_{N-1, K-N, 1-\alpha/2}}$$

where N = number of patients and K = number of measurements.

In order to be included in the test-retest calculations, a patient has to have non-missing cluster scores at both visit 1 and visit 2.

ICC values < 0.4 will be considered to represent poor reliability, values > 0.75 excellent reliability, and values in between fair to good reliability (Fleiss 1986).

Missing values

If a patient answered less than 50% of the items in a cluster, the cluster score will be set to missing.

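### Section 6.3.3 lets an exploratory solution replace the five QOLRAD dimensions on in-sample fit, and unpenalised fit of that kind is no evidence against the original

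*Protocol*

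**What the plan says.** Protocol section 4.2.5.1 describes the parent instrument: "The QOLRAD consists of 25 items addressing concerns associated with gastrointestinal symptoms, combined into five dimensions". It also reports that this factor structure has been confirmed in GERD populations. The same section explains that the symptom wording was changed for this study.

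Section 6.3.3 re-derives the structure by exploratory analysis "using the item responses at visit 1". The method is: "Principal components factor analyses with varimax and oblimin rotation will be used". It continues: "The factor structure of the modified QOLRAD will be compared to the original QOLRAD heartburn version". The decision rule is: "If a new factor structure for the modified QOLRAD is a better fit for the study population, this new factor structure will be used".

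The outcome carries forward. Section 6.3.5.1 states: "The ICC will be calculated for the derived clusters of the modified QOLRAD obtained through the factor analysis". Section 6.3.5.2 says that alpha "will be calculated for each multi-item cluster derived through the factor analysis described in section 6.3.3". Sections 6.3.6.1 and 6.3.6.2 also use the derived clusters for convergent, discriminant and known-groups validity. Section 4.2.5 adds that "specific impact dimensions (e.g. sleep and food/drink) will be used as reference when establishing the clinically meaningful change" of the RDQ e-diary.

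Under section 6.2, all enrolled patients with data enter the Part 1 analyses, so there is no split into derivation and test samples. Section 6.1 announces a SAP for analyses of Part 2 data. The rule for Part 1 is therefore the one written here.

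**The concern.** The new structure is tuned to the visit 1 responses and is then compared with the original on those same responses. A flexible solution has a built-in advantage in that comparison. Without a penalty, a confirmatory test or fresh data, winning it does not show that the original dimensions are wrong for this population.

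At stake is what the reliability and validity results describe. If the items are regrouped, ICC, alpha and validity are specified only for the new clusters. They can then no longer be set beside the earlier QOLRAD evidence. The sleep and food/drink references for the RDQ clinically meaningful change would rest on dimensions whose properties this study need not report. Section 1.2 carries the measures into phase IIB and III, so a grouping specific to this sample would go with them.

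**Working it through.** The protocol gives no figure for this decision, so there is none to reproduce. The precision and power figures in section 6.6 concern alpha, the ICC and complete resolution.

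**Inputs from the protocol.** There are 25 items in dimensions of 6, 5, 6, 5 and 3 items, each scored 1 to 7 (sections 4.2.5.1 and 4.2.5.2), and 500 patients in Part 1 (section 6.6).

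**Assumed inputs.** The protocol gives no loadings, no correlations between dimensions and no rule for the number of components, so all of these are assumptions.

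**Step 1: nesting.**
- Distinct variances and covariances: 25 × 26 / 2 = 325.
- Original five-dimension model: 25 loadings + 25 residual variances + 10 correlations = 60 parameters, df = 325 − 60 = 265.
- Unrestricted five-factor model: 25 × 5 + 25 − (5 × 4 / 2) = 140 parameters, df = 325 − 140 = 185.
- The first is a special case of the second, so the second cannot fit the same data worse. If the original is true, the expected chi-square gain is about 265 − 185 = 80.
- Variance explained behaves the same way: the first five principal components explain at least as much as any five item scores.

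**Step 2: original structure true, 500 runs per setting** (loadings 0.75 or 0.85, equal factor correlations 0.5, 0.7 or 0.8).
- Same data, unpenalised (likelihood discrepancy, residuals, variance explained): the exploratory solution was better in 100% of runs. The margin in variance explained was trivial, for example 0.632 against 0.631.
- Independent sample of 500: better in about 0% (likelihood) and 0-1% (residuals).
- Same data, penalised: about 0%. AIC needs a gain above 2 × 80 = 160, and P(chi-square on 80 df > 160) is about 3 × 10⁻⁷. BIC needs a gain above 80 × ln 500 ≈ 497.

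**Step 3: does the item grouping change?** In the Step 2 settings, highest-loading assignment after varimax with five components returned the original dimensions in 100% of runs. The clusters would then be the original scores and nothing would be replaced. With eigenvalue > 1 retention (assumed), the original grouping came back in 100% of runs at correlation 0.5, about 50% at 0.7 and 0% at 0.8. The mean number of components kept was 5.0, 4.5 and 3.4.

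**Step 4: do those misgroupings also fit better?** No. With loadings of 0.7-0.9 and equal correlations of 0.6, 0.7, 0.75, 0.8 and 0.85 (200 samples each), the grouping differed in 0, 120, 193, 200 and 200 samples, 713 in all. The retained components explained more variance than the five original scores in 0 of 713. A separate simulation in the same kind of setting gave 0 of 516.

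**Step 5: unequal correlations.** The original stays true, but the 3-item vitality dimension is assumed to correlate 0.88 with two others. Five components then gave a different grouping in 57% of samples, and in 95% with loadings of 0.55-0.85. Every one of these beat the original on in-sample variance explained, as Step 1 requires. The percentages also depend on the correlations assumed among the other dimensions.

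**Step 6: are high correlations plausible?** Section 4.2.5.1 quotes alphas of 0.89 to 0.97 across subscales and total, without saying which belongs to the total.
- Mean inter-item correlation = alpha / (25 − 24 × alpha). For 0.97 this is 0.97 / 1.72 = 0.564; for 0.96 it is 0.96 / 1.96 = 0.490.
- Of 300 item pairs, 15 + 10 + 15 + 10 + 3 = 53 lie within dimensions and 247 between.
- Assume a within-dimension item correlation w of 0.65 to 0.75. The implied average correlation between dimensions is (300 × mean − 53 × w) / (247 × w).
- Result: 0.84 to 0.70 for a total alpha of 0.97, and 0.70 to 0.58 for 0.96.

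This is an average. It neither shows nor excludes a single pair near 0.88.

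**The case against.** The strongest objection is that the rule needs two things together: a new grouping, and a better fit. In the equal-correlation, high-loading setting they never coincide. Five components guarantee better fit but return the original grouping; fewer components change the grouping but fit worse. This stands. A reader might infer from the eigenvalue > 1 results that the validated scoring would be lost almost every time dimensions correlate at 0.8. Step 4 shows that those results do not support this. The objection fails once correlations are unequal (Step 5), or if the observed grouping is itself read as the better fit, which the wording does not exclude.

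Second, the protocol does not commit to an unpenalised measure, and AIC or BIC would protect the original. An unnamed index or retention rule is also ordinary detail for a later plan. That is fair, and the missing name alone would not be worth raising. What the protocol does fix is the rule itself, exploratory analysis as the only stated method, and results specified for the derived clusters only.

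Third, the wording and the population have changed, so re-examining the structure is legitimate. This stands; the fault lies in the decision rule.

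Fourth, the original dimensions do not cease to exist. All 25 items are still collected, and section 6.3.1 itself uses three of the original dimensions. This also stands. The loss is that their reliability and validity in this study need not be reported.

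**Conclusion.** The point holds in limited form. Better fit on the visit 1 data, if unpenalised, carries no information against the original five dimensions, and nothing stated in section 6.3.3 rules out that reading. A correct structure could therefore be replaced, but the documents do not show that it would be.

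How likely this is depends on facts the documents do not give. The risk is nil in the equal-correlation, high-loading setting if five components are kept. It is 57% to 95% under the assumed 0.88 correlations, if that grouping is adopted on variance explained. These figures illustrate the mechanism and do not forecast what will happen. The grouping checks used varimax; oblimin, which the protocol also plans, may group items differently.

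The change is worth making because the rule feeds every QOLRAD reliability and validity result and the remedy is cheap. It does not affect the safety of patients or the randomised comparison.

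**What to change.** In section 6.3.3:
- Make the original five dimensions the default scoring.
- Fit them, and any alternative from the exploratory analysis, as confirmatory models.
- Replace the original only if the alternative is better on a penalised index named in advance, such as BIC.
- Optionally, derive the alternative in one random half of the patients and require it to win in the other. This matters most if the alternative also has five clusters with each item in one: both models then have 60 parameters, the penalties cancel, and only fresh data remove the advantage of having chosen the grouping on the same responses.

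In sections 6.3.5 and 6.3.6, report ICC, alpha, convergent and discriminant validity, and known-groups validity for the original five dimensions whatever the outcome. This keeps the link to earlier QOLRAD evidence and supports the sleep and food/drink references for the RDQ.

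In a check of the split-half version with BIC, the true original was kept in 136 of 136 samples where eigenvalue > 1 had misgrouped the items. That check had the original true throughout, so it does not show how well a genuinely changed structure would be detected.

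The cost is wording and one extra analysis of data already collected. With the hold-out, the alternative is derived on about 250 patients instead of 500.
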